4.6.6.2 Presentation

The number and percentage of participants with suicidal ideation (overall and by maximum category), suicidal behavior (overall and by maximum category), and no suicidal ideation or behavior will be given for assessments during screening, during treatment and follow-up period, respectively.

Furthermore, descriptive statistics on the total number of attempts, total number of interrupted attempts, and total number of aborted attempts will be summarized for attempts during screening, during treatment and follow-up period, respectively.

4.6.7 Cushingoid features

4.6.7.1 Definition and Derivations

Cushingoid features include moon face, buffalo hump, purple or violaceous striae, central obesity, hirsutism, acne, easy bruising, and fragile skin.

4.6.7.2 Presentation

The number and percentage of participants are explored for each feature by visit during the treatment period. For participants with baseline OCS ≥ 10 mg/day prednisone or equivalent, the summary is repeated by maintained OCS reduction at Week 52 (yes versus no) as defined in Section 4.2.3.1).

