3.3 General Considerations

- Summary tables are produced by treatment group (Anifrolumab 300mg and Placebo) unless otherwise stated. Total columns are produced only for tables of study population data, unless otherwise stated.
- Continuous variables are summarized by the number of non-missing observations, mean, standard deviation (SD), median, and the minimum and maximum as appropriate.
- Log-transformed continuous variables are summarized in a similar manner. The geometric mean and coefficient of variation (CV%), median, minimum and maximum are

presented as appropriate. In addition, the relative change from baseline is calculated by back-transforming the change from baseline of the logarithmic variable as necessary.

- Categorical variables are summarized as counts (n) and percentages (%). Unless otherwise stated, percentages are calculated using the relevant analysis set population total by treatment group as the denominator. Percentages are rounded to one decimal place; except 100% which are displayed without any decimal places. Percentages are not to be presented for zero counts.
- If a model is used to estimate the treatment difference, the corresponding confidence interval (CI) according to the model is presented. Otherwise, the unadjusted CI is used.
- Mean, SD, medians, 1st quartile and 3rd quartile are rounded to one additional decimal place relative to the original data, the maximum, minimum will be displayed with the same accuracy as the original data and the CV% is presented with 1 decimal place. The statistics are displayed in the order of n, mean, minimum, first quartile (optional), median, third quartile (optional), maximum. 95% CIs are presented for treatment comparison to one more decimal place than the raw data. For the confirmatory treatment comparisons, p-values will be reported to 3 decimal places. Percentages (proportion) will be rounded to one decimal place.
- Summaries are provided by time point of assessment where appropriate. Where summaries are by time point, study day is calculated in relation to the date of first dose of study treatment. For assignment of data to time points using the visit windows, study day is calculated in relation to the date of first dose of investigational product.
- Study Day 1 is defined as the day of first study drug administration.
- Study Days prior to the date of first study drug administration, are defined as:
(Date of assessment – date of first administration of IP)

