4.2.3.3 Handling of Dropouts and Missing Data

If any of the conditions cannot be evaluated at Week 52 (e.g., due to missing values) the participant is considered as not reaching a maintained OCS reduction.

If there is no assessment in Week 40 window, then the target date for the timepoint will be used instead.

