4.2.8.4 Primary Analysis of Other Secondary Endpoint – immunogenicity

If not stated otherwise, all analyses of ADA are performed for the safety analysis set by IFN 4-gene test status (high/low/overall).

The proportion of participants with ADA results as described in Section 4.2.9.1 will be presented. Summary statistics will be provided for titer of ADA positive participants by timepoint. Descriptive statistics will include n (number of reportable titers), minimum, quartiles (1st quartile, median, 3rd quartile) and maximum. For the summary of participants who are ADA positive by visit or at a single visit point, the denominator for percentages is the number of participants with an adequate sample that provides a reportable result of positive or negative for the respective visit. For the summary of overall ADA categories (e.g., ADA positive at any time), percentages will be based on participants with at least one ADA result during the study.

The percentage of participants with positive ADA results by timepoint will be presented graphically in a line plot. ADA titres-time profiles (line plots of median and quartiles by time point) will be generated for the anifrolumab treatment group.

Variables of proportions regarding neutralizing antibodies will be summarized presenting the number and percentage of the categories given in Section 4.2.9.1.

Key subject information for participants with an ADA positive result at any time and for participants with ADA incidence and had ADA titres increase by at least 4-fold from onset to maximum titre will be provided.

The analyses of impact of ADA on PK were described in section 4.2.7.4 and on PD endpoints are described in section 4.2.9.4. Potential association of ADA with safety and efficacy may be explored by subgroup analyses. Endpoint wise subgroup analyses for efficacy and safety may be performed.

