4.2.10.3 Handling of Dropouts and Missing Data

If any of the BILAG organ system grade results cannot be evaluated at any visit up to Week 52 (e.g., due to missing values), the data for that criterion is to be imputed using LOCF to determine the current BILAG organ system grade. This applies only once. For example, if any of the Week 52 organ system grade result is missing and Week 48 data is not missing, the missing Week 52 organ system grade result will be imputed using the corresponding Week 48 data. Otherwise the participant's BILAG-2004 is missing at Week 52. Local laboratory results will not be requested. If lab data is missing for 2 sequential visits, N/A is indicated for the organ system grade.

LOCF records are not used in the repeated measures models.

4.2.10.4 Primary Analysis of Exploratory Endpoints – individual components of BICLA response and SRI response

Individual components of BICLA and SRI(4) and rate of no ICEs at weeks 24 and 52 together will be presented in a table by treatment group.

Change from baseline in SLEDAI-2K and PGA will be analyzed using repeated measures models with fixed effects for baseline value, treatment group, visit, treatment*visit interaction and stratification factors, and participant as random effect. Covariance parameters will be estimated using restricted Maximum Likelihood method and Kenward Rogers denominator degrees of freedom will be used for the tests of fixed effects. An unstructured covariance matrix will be used. In case of convergence issues, the following alternative structures will be used for fitting (in that order): Heterogeneous Toeplitz, heterogeneous AR(1), Heterogeneous CS, Homogeneous CS. Results will be presented for each visit in terms of the adjusted means for each treatment group, estimates of treatment differences, and associated 2-sided CIs.

For each SLEDAI organ system (central nervous system, vascular, musculoskeletal, renal, mucocutaneous, cardiovascular system and respiratory, immunology, and hematological and fever) the number and percentage of participants with an improvement at Week 24 and

Week 52, respectively, will be given for participants with corresponding organ system involvement at baseline.

For BILAG-2004, the number and percentage of participants with a score of A, B, and C, D, or E, respectively, will be given by visit for the following organ systems:

- Constitutional
- Mucocutaneous
- Neuropsychiatric
- Musculoskeletal
- Cardiorespiratory
- Gastrointestinal

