4.2.17.4 Not applicable. Primary Analysis of Exploratory Endpoint – EQ-5D-5L

The 5 dimensions of EQ-5D-5L (mobility, self-care, usual activities, pain/discomfort, and anxiety/depression) are summarized by timepoint as number and percentage of participants with the different health states.

Observed values and changes from baseline in VAS Score and single summary utility index, respectively, are presented longitudinally with descriptive statistics.

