4.2.18.4 Primary Analysis of Exploratory Endpoint – WPAI-Lupus

At each scheduled visit, the number and percentage of participants employed are presented. Observed values and changes from baseline in hours missed due to lupus and in WPAI scores (absenteeism, presenteeism, work productivity loss and activity impairment) are presented longitudinally with descriptive statistics.

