4.6 Safety Analyses

The following safety data are collected: vital signs, physical examination, 12-lead ECGs, clinical laboratory tests (including haematology, clinical chemistry, urinalysis and lipid profile), C-SSRS, Cushingoid features and AEs (including AEs of specific interest [AESIs]).

Safety analyses are performed using the safety analysis set. Unless otherwise specified, safety data are presented using descriptive statistics during the treatment and follow-up period.

Change from baseline to each post-treatment time point where scheduled assessments were made to calculate for relevant measurements.

If not stated otherwise, on-treatment values are defined as values with an assessment date after the first administration of IP and on or before the date of last administration of IP + 28 days.

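### By-visit percentages for Cushingoid features, BILAG-2004 grades, EQ-5D-5L states and employment default to the whole analysis set, so missing assessments pull every percentage down

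*SAP*

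**What the plan says.** SAP 3.3 sets a general rule: "Unless otherwise stated, percentages are calculated using the relevant analysis set population total by treatment group as the denominator". The analysis sets in SAP 3.2 are fixed populations, and none is specific to a visit.

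Four by-visit displays of observed categories state no visit-specific denominator:

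- Cushingoid features (4.6.7.2): "The number and percentage of participants are explored for each feature by visit during the treatment period". The analysis set comes from 4.6: "Safety analyses are performed using the safety analysis set".
- BILAG-2004 grades (4.2.10.4): "the number and percentage of participants with a score of A, B, and C, D, or E, respectively, will be given by visit".
- EQ-5D-5L (4.2.17.4): the dimensions "are summarized by timepoint as number and percentage of participants with the different health states".
- Employment (4.2.18.4): "At each scheduled visit, the number and percentage of participants employed are presented". The derivations in 4.2.18.2 list the percentage employed out of all participants.

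SAP 3.3.1.3 leaves missing data unimputed unless a section says otherwise, and 3.3.2 leaves an empty visit window missing. For BILAG grades, 4.2.10.3 allows one carry-forward step, after which the grade is missing. For EQ-5D-5L and work productivity, the missing-data sections (4.2.17.3, 4.2.18.3) are marked as not applicable.

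Elsewhere the SAP departs from its default. For anti-drug antibodies by visit (4.2.8.4), "the denominator for percentages is the number of participants with an adequate sample that provides a reportable result". Treatment-emergent laboratory and vital-sign changes (4.6.3.2, 4.6.5.2) use participants with a baseline and a later measurement. Anti-dsDNA (4.2.9.4) shows missing as its own category.

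**The concern.** Where the authors wanted a different denominator, they wrote one. A programmer following the text would therefore use the full arm total in these four tables. A participant who missed the visit or has left the study is then counted in the base but in none of the rows.

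For a yes/no finding such as moon face, that has the same numerical effect as recording the finding as absent. The prevalence of a steroid-related harm falls as attendance falls, and the arm with poorer attendance looks better for no clinical reason. Protocol 5.2.2.4 collects these features to see whether they resolve as steroids are reduced, so a fall over time produced by missing visits would be easy to misread.

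EQ-5D-5L has a known loss as well as ordinary dropout. SAP 3.3.9 removes records from mainland China and Taiwan sites collected before software version 7.0, and SAP 4.7 expects about 80% of participants to come from mainland China.

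**Working it through.** The documents give no percentage for these tables and no dropout rate, so there is no planned figure to reproduce. The arithmetic shows what the rule does under assumed rates.

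**Inputs.** 260 randomised 1:1 (Protocol 8.2), so 130 per arm; about 80% from mainland China (SAP 4.7). Assumed: prevalence p among those assessed, and fraction assessed f.

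**Formula.** Shown percentage = p × f. With the number assessed as denominator it is p. If p is equal in both arms, the false difference is p × (f1 − f2).

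**Cushingoid features, 90% versus 80% assessed**

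- Assessed: 130 × 0.90 = 117 and 130 × 0.80 = 104.
- At p = 20%: 0.20 × 117 = 23.4, and 23.4/130 = 18.0%; 0.20 × 104 = 20.8, and 20.8/130 = 16.0%. The false difference is 2.0 points.
- At p = 10%: 9.0% versus 8.0%, 1.0 point.
- At p = 30%: 27.0% versus 24.0%, 3.0 points.
- With 90% versus 85% assessed and p = 30%: 27.0% versus 25.5%, 1.5 points.

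**Employment.** If 50% of those answering are employed, with 90% versus 80% answering, the table shows 45.0% versus 40.0%. Here the arm with poorer attendance looks worse.

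**BILAG-2004 grades.** If a fraction f still has a grade after the single carry-forward step, every grade category is multiplied by f and the categories sum to 100 × f rather than 100. With f = 90% they sum to 90%.

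**EQ-5D-5L.** Let e be the share of mainland China records at a visit excluded under SAP 3.3.9. Ignore the Taiwan exclusion and other missingness, and take 80% mainland participants in each arm. The usable fraction is 0.20 + 0.80 × (1 − e).

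- e = 25%: 80% usable (104 of 130). A state held by half of those with data shows as 40%, and the five states sum to 80%.
- e = 50%: 60% usable (78 of 130); 30%; sum 60%.
- e = 75%: 40% usable (52 of 130); 20%; sum 40%.
- e = 100%: 20% usable (26 of 130); 10%; sum 20%.

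The documents do not say which e applies at any visit. Records from affected sites after version 7.0 are kept, so 100% is only the extreme.

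**The case against.** Several points on the other side stand.

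For BILAG-2004 grades and EQ-5D-5L states, a reader might infer that an unassessed participant is counted as healthy. The documents do not support that. Both are full category displays, so the participant drops out of every row, including the favourable one, and the shortfall from 100% is visible. BILAG grades also have the carry-forward step, so one missed visit following an assessed one has no effect.

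A reader might also infer that more dropout always flatters an arm. That direction holds for Cushingoid features only. Employment moves the other way and, under 4.2.18.2, follows a stated choice of base.

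The tempting stronger reading concerns the Cushingoid table split by maintained steroid reduction: that everyone without Week 52 data lands in the no group and masks the contrast. SAP 4.2.3.3 does say that when a condition cannot be evaluated, "the participant is considered as not reaching a maintained OCS reduction". But 4.2.3.1 and 4.2.3.3 fall back to the target date when no assessment falls in the Week 52 or Week 40 window, so a missed visit alone does not force a no. The split uses the 4.2.3.1 definition, which does not itself include stopping treatment, and Protocol 3.9.3 asks participants who stop treatment to keep attending. Taken literally, SAP 3.3 does not even give the subgroup as denominator. The dilution may fall more on the no group, to the extent that non-evaluable participants are placed there, but its size cannot be determined.

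Finally, counts accompany the percentages, the table shells are not in the documents, and SAP 3.3.9 might be read as narrowing what the EQ-5D-5L analysis covers. That section restricts which data are used, however; it does not redefine an analysis set. None of this supplies the missing denominator.

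**Conclusion.** The point holds as a defect in the stated rule for four descriptive tables. Followed as written, SAP 3.3 understates by-visit Cushingoid prevalence and percentage employed in proportion to missing assessments, and shrinks all BILAG-2004 and EQ-5D-5L categories so that they do not sum to 100%.

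Under the assumed attendance gap of 10 percentage points, the false arm difference is 1 to 3 points for a feature with 10% to 30% prevalence. The EQ-5D-5L effect could be much larger, with the states summing to about 60% if half the mainland China records at a visit are excluded. All attendance, prevalence and exclusion rates here are assumptions; only the rule, the 260 participants and the 80% share come from the documents.

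No hypothesis test depends on these tables.

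**What to change.** Add one sentence to SAP 3.3: by-visit summaries of observed categorical data use as denominator the participants in the analysis set, or in the displayed subgroup, who have a non-missing assessment at that visit, and that n is shown. A missing row, as already planned for anti-dsDNA, is an acceptable alternative.

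Name the sections covered: 4.2.10.4 (BILAG grades, after the carry-forward step), 4.2.17.4, 4.2.18.2 with 4.2.18.4 (participants answering Question 1 at that visit) and 4.6.7.2, including the split by maintained steroid reduction. Leave composite responder endpoints, where non-response is the stated rule, and cumulative adverse-event tables unchanged.

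The cost is one sentence and a table-shell change. Protocol 8.1 allows SAP amendments before unblinding. Percentages will be higher wherever assessments are missing. The change does not remove bias if those assessed differ from those not assessed, but the displayed n lets the reader see how much is missing.

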4.7 China Subpopulation Analyses

Approximately 80% of the participants are estimated to be recruited from mainland China. The efficacy and safety in China subpopulation (defined as all participants from sites in mainland China) were analyzed to facilitate a benefit-risk assessment for regulatory submission in China.

Efficacy are summarised for the China subpopulation, which consists of all randomized participants from sites in mainland China in the Full Analysis Set as defined in Section 3.2.2. Selected key analyses will be conducted and stratified analyses will not include the stratification factor region for the China subpopulation. These analyses are considered descriptive/supportive only, therefore no significance testing will be performed.

Safety and tolerability are summarised for the China subpopulation, which consists of all dosed participants from sites in mainland China in the Safety Analysis Set as defined in Section 3.2.3.

The PK data is summarised for the China subpopulation, which consists of all dosed participants from sites in mainland China in the Pharmacokinetic Analysis Set as defined in Section 3.2.4.

5 INTERIM ANALYSIS

No interim analysis is planned for this study.

7 APPENDIX

[Appendix A](#): Derivation of IFN21 parameters

[Appendix B](#): Reference Ranges and TELVC for Laboratory Values

[Appendix C](#): Reference Ranges and TELVC for Vital Signs

[Appendix D](#): Restricted and prohibited medications – Programmatic Rules

7.1 Appendix A - Derivation of IFN21 parameters

There are two IFN parameters to be calculated during the study; percent of baseline (BL) IFN 21-gene PD signature and the gene signature fold change.

The following steps should be implemented in the derivation of these parameters.

1. Calculate the mean Ct values for each gene and the three housekeeper genes (18S, ATCB and GAPDH) on the ThermoFisher TLDA platform (test and normal control samples) within a particular subject.

2. Calculate the mean Ct value of the three housekeeper genes;

$$HK_{mean} = mean(Ct_{18S}, Ct_{ATCB}, Ct_{GAPDH})$$

3. Calculate ΔCt values by subtracting the mean Ct value of the three housekeeper genes from each test gene:

$$\Delta Ct_{gene} = Ct_{test\ gene} - HK_{mean}$$

4. Calculate the ΔCt values for the normal control genes, as in Step 3.

5. Calculate $-\Delta\Delta Ct$ values as:

$$-\Delta\Delta Ct_{gene} = \Delta Ct_{normal\ control} - \Delta Ct_{test\ gene}$$

6. Linearize the $-\Delta\Delta Ct$ values for each gene as follows:

$$linearized_{gene} = 2^{-\Delta\Delta Ct}$$

7. Calculate the percent of baseline IFN 21-gene PD signature for each gene for each post-BL visit (Visit X) as:

$$\begin{aligned} \% \text{ of BL IFN21gene PD signature}_{gene} &= 100 - \left(\left(\frac{2^{-\Delta\Delta Ct_{BL}} - 2^{-\Delta\Delta Ct_{visit\ x}}}{2^{-\Delta\Delta Ct_{BL}}} \right) \times 100 \right) \\ &= \left(\frac{2^{-\Delta\Delta Ct_{visit\ x}}}{2^{-\Delta\Delta Ct_{BL}}} \right) \times 100 \end{aligned}$$

The final % of baseline IFN 21-gene PD signature for each timepoint, for each participant, is the median of the individual gene % of baseline IFN 21-gene PD signature values calculated in Step 7. There will be one value per participant per post-Visit 1 visit:

$$Overall \% \text{ of baseline IFN 21 gene PD signature} = median(\% \text{ of BL IFN 21 gene PD signature}_{gene})$$

The fold change for each timepoint and each participant is the median of the linearized values for each gene, calculated in Step 6:

$$\text{Fold Change} = \text{median}(2^{-\Delta\Delta Ct})$$

Redacted for Public Disclosure

7.2 Appendix B - Reference Ranges and TELVC for Laboratory Values

Parameter	Unit	Low value	Low decrease	High value	High increase
Haematology					
Hemoglobin	g/L	≤60	NA	≥200	NA
		≤70 and decrease from BL ≥15			
Hematocrit	V/V	≤0.18	NA	≥0.64	NA
		≤0.21 and decrease from BL ≥15%			
WBC	10E9/L	≤2, <1	NA	≥20	NA
Neutrophils	10E9/L	<0.5	NA	≥20	NA
		<1.0 and decrease from BL ≥0.5			
Lymphocyte	10E9/L	≤0.5, ≤0.25	NA	≥10.0	NA
Monocytes	10E9/L	NA	NA	≥1.4, ≥5.0	NA
Eosinophils	10E9/L	NA	NA	≥1.5, ≥5.0	NA
Basophils	10E9/L	NA	NA	≥1.0, ≥2.0	NA
INR		NA	NA	≥4.5	NA
Platelet	10E9/L	≤20	NA	≥600	NA
		≤50 and decrease from BL ≥25			
Biochemistry					
ALT	IU/L	NA	NA	≥3 x ULN, ≥5 x ULN	NA
AST	IU/L	NA	NA	≥3 x ULN, ≥5 x ULN	NA
ALP	IU/L	NA	NA	≥3 x ULN NA	NA
CK	IU/L	NA	NA	≥500, ≥2000	NA
GGT	IU/L	NA	NA	≥5 x ULN	NA
Total bilirubin	μmol/L	NA	NA	≥2 x ULN	NA
Albumin	g/L	≤20	NA	≥100	NA
		≤25 and decrease from BL ≥10		≥70 and increase from BL ≥10	
BUN	mmol/L	NA	NA	≥18	NA

Creatinine	umol/L	NA	NA	≥140, ≥190	NA
Sodium	mmol/L	≤132	NA	≥152	NA
Potassium	mmol/L	≤3	NA	≥5.5	NA
Chloride	mmol/L	≤90	NA	≥120	NA
Fasting Glucose	mmol/L	≤2.5	NA	≥7.0, ≥11.1	NA
Total Cholesterol	mmol/L	NA	NA	≥7.25	NA
Urinalysis					
Ketone Bodies/ Qualitative Erythrocytes/ U- Glucose					Negative/positive at baseline to ++, +++, +++++ at any post- baseline value Increase from baseline of at least ++ at any post-baseline value
Urine protein/ creatinine ratio	g/mmol	NA	NA	≥0.395	NA
Urine protein					Increase ≥ ++ ≥ ++ with BL negative, TRACE, or +
Fasting lipid profile					
HDL	mmol/L	≤0.8	NA	NA	NA
LDL	mmol/L	NA	NA	≥5.2	NA
Triglycerides	mmol/L	NA	NA	≥3.6, ≥5.4	NA

7.3 Appendix C - Reference Ranges and TELVC for Vital Signs

Parameter	Unit	Low value	Low decrease	High value	High increase
Pulse	Beats per minute	≤ 50 ≤ 50 and decrease from BL ≥ 20	NA	≥ 120 ≥ 120 and increase from BL ≥ 20	NA
Systolic blood pressure	mmHg	≤ 90 ≤ 90 and decrease from BL ≥ 20	NA	≥ 160 ≥ 160 and increase from BL ≥ 20	NA
Diastolic blood pressure	mmHg	≤ 50 ≤ 50 and decrease from BL ≥ 10	NA	≥ 100 ≥ 100 and increase from BL ≥ 10	NA

